7.1. Sample Size Determination

Sample size considerations were framed using standard study design parameters to ensure 80% power to detect pre-specified effect sizes utilizing intermediate outcomes. However, for this early phase pilot study, the primary focus is directed at assessing safety and feasibility, with no attempt to create critical test result regions for standard hypothesis testing.

From preliminary studies, we assumed estimated baseline parameters of E' to be 5.8 ± 1.8 cm/s.^{34, 43, 87, 88} Assuming a correlation ≥ 0.2 between pre and post-therapy E' , and a 10% dropout rate of study participants by the end of the study, a sample size of 125 (2:3; 50 patients for the placebo arm and 25 per SPL dose x 3 active treatment arms) will provide 80% power to detect effect size of 0.7SD (1.3 cm/sec) difference in change from baseline to 9 month endpoint in E' , equivalent to a 22% average reduction across the 3 active SPL treatment arms. Short-term studies with SPL in diabetes were consistent with an effect of this magnitude⁵⁴.

For the safety endpoint of hyperkalemia incidence, we assumed a 5% incidence in the placebo arm. With a sample size of 125, derived under the effect size considerations noted previously, this design provides 80% power to detect an average incidence of 22% across the 3 SPL dose arms. Moreover, this same sample size also provides 80% power to detect a small difference of 0.1 mEq/L in time-averaged serum potassium concentration, treated as a continuous variable, between placebo and treatment arms.

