7.4.1. Descriptive Analyses and Primary Efficacy and Safety Analyses

Standard descriptive statistics will be used to summarize baseline characteristics and study outcome measures at each follow-up visit, both overall, and within each treatment group.

Examination of baseline characteristics will include estimates of the distribution of age, race, and other demographic characteristics, lab measures and study center. Summary statistics such as means, medians, and ranges will be produced for all measured variables.

Frequencies will be computed for all categorical and ordinal variables. Graphical methods including stem-and-leaf diagrams and boxplots will be used to examine distributions, identify potential influential points, and guide in the choice of transformations, if warranted. The balance of baseline measures across the three treatment groups will be compared using appropriate k-sample tests, including Kruskal-Wallis tests and Fisher's exact tests.

Analysis of Primary Efficacy and Safety Outcomes Mean (\pm standard deviation) or median (interquartile values) of baseline and end of study measurement in the primary endpoint E' will be presented. Change in E' velocity at 36 weeks will be assessed and reported quantitatively, and descriptive statistics for absolute and % change will be provided. Mixed effects linear regression models with baseline covariate adjustments will be used for assessment of treatment effects. Model assumptions regarding homoscedasticity and normality will be examined using standard techniques.

For the primary safety endpoint, tables with percent incidence and incidence rate (for events that can occur more than once during follow-up) will be prepared. Differences in incidence and incidence-rate will be assessed using logistic regression or Poisson regression with factors for assigned treatment and the stratification variable. In particular, for safety endpoints, we will investigate the potential change in potassium level in placebo and treatment groups with monthly measure of potassium. Mixed effects linear regression models will be used to assess the direction and time averaged magnitude of change in potassium, with and without controlling for baseline covariates. The proportion of serious hyperkalemia in treatment and placebo groups will be compared with Chi-square test or Fisher's exact test.

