The primary analysis will examine the intention to treat population. All analyses will be repeated in the as-treated, all-treated and per-protocol populations (see **Section 7.3**). Secondary endpoint analyses will be presented using analogous techniques. $P < 0.05$ will be considered

significant in all analyses.

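### The Poisson comparison of repeatable safety-event rates names nothing to handle repeat events in the same participant, so its default standard errors can be too small

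*Combined protocol and SAP*

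**What the plan says.** Section 7.4.1 of the combined protocol and SAP says that for the primary safety endpoint "tables with percent incidence and incidence rate (for events that can occur more than once during follow-up) will be prepared". It then gives the method of comparison: "Differences in incidence and incidence-rate will be assessed using logistic regression or Poisson regression with factors for assigned treatment and the stratification variable". A logistic model handles whether a participant had any event. Poisson regression is therefore the only method named for a rate of repeatable events.

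The same section tests serious hyperkalemia by Chi-square or Fisher and keeps mixed models for E' and potassium level. It applies a 0.05 significance threshold to every analysis, repeats the analyses in three further populations, and treats secondary endpoints analogously. The opening of Section 7.4 calls the methods an overview that may be revised.

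Section 3.2.1 defines the two primary safety endpoints (potassium above 6.5 mEq/L, serious hypotension) as incidences. Section 7.1 powers hyperkalemia as a proportion of participants: "we assumed a 5% incidence in the placebo arm", with "80% power to detect an average incidence of 22% across the 3 SPL dose arms". Nowhere do the documents mention overdispersion, a scale parameter, clustered variance, a negative binomial model or a participant effect for event counts.

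**The concern.** Poisson regression with its default variance assumes that the variance of a participant's count equals its mean. The documents give reasons to expect more spread than that:

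- Section 5.3 names dialysis vintage and ACEI/ARB use as raising hyperkalemia risk. Adjustment removes only that measured part.
- Section 6.9 lists other causes that belong to the individual: access problems, missed or shortened sessions, diet.
- Section 6.9 requires a recheck within a week once potassium reaches 6.0 mEq/L. One high value thus brings an early chance of another, and no rule says whether that is a new event.
- Section 3.2.2 defines intra-dialytic hypotension as a recurrent condition within a person.
- Section 7.3 assigns as-treated safety events to the dose in use at the time, so one participant can contribute events and time at several doses.

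At stake are the p values and confidence intervals for event rates in a pilot that is meant to inform dose choice and later trials. Too small a standard error can produce a false difference between spironolactone and placebo, or an interval that looks more precise than it is.

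**Working it through.** **Inputs from the documents.** 50 placebo and 75 spironolactone participants (25 per dose); 5% placebo hyperkalemia incidence; 22% detectable average incidence; 10% dropout (all Section 7.1); alpha 0.05 (Section 7.4.1), taken as two-sided because sidedness is not stated. About 14 scheduled potassium values per participant allow repeat events: 3 escalation kits × 2 = 6, plus 8 visits from week 8 to week 36.

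**Assumptions.** k, the between-participant (frailty) variance left after adjustment, is 1, 2 or 4; the documents give no value. One event per person is assumed for commoner repeatable events such as potassium of at least 6.0 mEq/L.

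**The plan's own figure.** The stated 80% power for 5% v 22% reproduces as a comparison of proportions. The Chi-square test on 50 v 75, by exact enumeration, gives 80.6%. The unpooled normal formula after dropout gives SE = √(0.05×0.95/45 + 0.22×0.78/67.5) = 0.060; 0.17/0.060 − 1.96 ≈ 0.87; power 80.9%. Other variants are lower or higher (pooled 76.7%, Fisher 76.3%, arcsine 82.1%, all on 50 v 75). The figure counts each participant once and says nothing about the rate model. The documents give no power figure for a rate comparison.

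**Size by formula.** With mean count μ and gamma frailty variance k:

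- Var(count) = μ(1 + kμ), so default SE / true SE = 1/√(1 + kμ).
- Actual two-sided alpha = 2[1 − Φ(1.96/√(1 + kμ))].
- If a proportion p has any event, (1 + kμ)^(−1/k) = 1 − p, so 1 + kμ = (1 − p)^(−k).

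At p = 0.22 and k = 2, 1 + kμ = 0.78^(−2) = 1.644. The SE ratio is 0.78, and alpha = 2[1 − Φ(1.529)] = 0.126.

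| Setting (same in both arms) | k | 1 + kμ | SE ratio | Alpha by formula |
|---|---|---|---|---|
| 5% with any event | 1 / 2 / 4 | 1.05 / 1.11 / 1.23 | 0.97 / 0.95 / 0.90 | 5.6% / 6.3% / 7.7% |
| 22% with any event | 1 / 2 / 4 | 1.28 / 1.64 / 2.70 | 0.88 / 0.78 / 0.61 | 8.3% / 12.6% / 23.3% |
| 1 event per person | 1 / 2 / 4 | 2 / 3 / 5 | 0.71 / 0.58 / 0.45 | 16.6% / 25.8% / 38.1% |

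**Simulation** (50 v 75, no true difference, 20,000 to 40,000 trials per setting, no adjustment for strata). The test is a Wald test on the log rate ratio. The default variance is 1/A + 1/B, with A and B the event totals. The robust variance adds, for each arm, the sum of squared deviations of participants' counts from the arm mean, divided by the squared arm total.

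| Setting | k | Default Wald | Robust Wald |
|---|---|---|---|
| 5% with any event | 0 / 1 / 2 / 4 | 0.7% / 0.9% / 1.2% / 1.7% | – |
| 22% with any event | 1 / 2 / 4 | 7.6% / 11.6% / 22.5% | about 5% to 7% |
| 1 event per person | 1 / 2 / 4 | 16.3% / 25.5% / 37.5% | 5.8% / 6.4% / 7.4% |

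Repeat runs agree to within about half a percentage point.

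**Why 5% differs from the formula.** The formula is a large-sample one, and at 5% events are too few for it. The Wald test is conservative. The likelihood-ratio test rejects in 7.2% / 8.0% / 8.5% / 9.5% of trials for k = 0 / 1 / 2 / 4. Since 7.2% occurs with no clustering at all, most of that excess is sparse data. The chance that an arm has no event is 0.95^50 + 0.95^75 − 0.95^125 = 0.077 + 0.021 − 0.002 ≈ 10%. For placebo against one dose arm it is 0.95^50 + 0.95^25 − 0.95^75 = 0.077 + 0.277 − 0.021 ≈ 33%. In those trials neither variance rescues the log rate ratio.

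**The case against.** The plan says Poisson regression and states no variance estimator. Poisson with a sandwich variance would satisfy the sentence as written, and Section 7.4 leaves room to revise. This stands in part: the gap is one of specification, and a reader who infers that the plan commits to the model-based variance goes further than the text. But leave to revise does not supply a method, and a variance chosen after the counts are seen is a discretionary choice that can move a result across 0.05.

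A reader might also infer that the primary safety comparison as a whole is too optimistic. The documents do not support that. The primary endpoints are incidences, powered as proportions, and logistic regression of any event counts each participant once, as do the Chi-square and Fisher tests. Only the accompanying rate comparison is exposed. Nor do the documents support rates near one event per person for hyperkalemia above 6.5 mEq/L: the one placebo incidence given is 5%, where clustering matters little.

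The exclusions in Section 4.2 (recent high potassium, unscheduled dialysis, intra-dialytic hypotension), the dose reductions and discontinuations in Sections 6.8 and 6.9, and the stratification terms may all reduce recurrence or leftover heterogeneity. That stands, and is why k is shown as a range. With k = 0 there is no understatement. The absence of the word offset is no error in itself, since an incidence rate already implies person-time.

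Finally, Section 7.1 disclaims formal critical regions for this pilot. Yet Section 7.4.1 sets a 0.05 threshold for all analyses, and interval width matters in a pilot whatever the role of testing.

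**Conclusion.** The point holds for incidence-rate comparisons of repeatable events and for nothing else. If the default Poisson variance is used, standard errors are too small whenever participants differ in residual risk.

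For k between 1 and 4, with 50 v 75 and no true difference:

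- At the plan's 5% incidence there is little or no inflation from clustering (Wald 1% to 2%; likelihood-ratio 8% to 9.5%, of which about 7 points come from sparse data alone).
- At 22% incidence in both arms, type I error is about 8% to 22%.
- At an assumed one event per person it is 16% to 37%.

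The range of k and the one-event rate are assumptions; the 5% and 22% are the plan's. The practical exposure is therefore in the commoner repeatable secondary events, such as potassium of at least 6.0 mEq/L, rather than in the rare primary ones. The change should be made, but the sample size and the participant-level safety comparisons do not depend on it.

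**What to change.** In Section 7.4.1, state that incidence rates of repeatable events will be compared by Poisson regression with participant-level robust (sandwich) variance, or by negative binomial regression, with log follow-up time as offset. Where as-treated follow-up is split by dose, cluster on participant. Where an arm has few or no events, rely on the participant-level incidence comparison with an exact method.

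The cost is one or two sentences and slightly wider intervals. Without clustering, results barely change: at one event per person and k = 0, robust type I error is 5.2%. The remedy is not perfect in small arms under strong clustering. With k = 4, robust error is about 7% for 50 v 75. For placebo against a single dose arm (50 v 25) it is 8.1% at 22% incidence and 8.8% at one event per person.

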3.1. General Design

This is a randomized, placebo-controlled 4-arm trial that will compare placebo with 3 doses of SPL. Participants will be randomized in a 2:1:1:1 fashion to placebo or SPL, with equal proportions randomized to each of 3 SPL doses: 12.5, 25 or 50 mg once daily. As shown in **Figure 1**, the study will be conducted in 2 phases – a dose escalation phase and a treatment phase.

All participants randomized to SPL will initiate treatment at 12.5 mg daily. Participants will be evaluated weekly for tolerability, hypotension and hyperkalemia. At 2 weeks, if the initial dose has been tolerated, participants randomized to the 25 or 50 mg SPL arm will increase the dose to 25 mg for 2 weeks with weekly evaluation for tolerability, hypotension and hyperkalemia. Participants randomized to 12.5 mg SPL or placebo arm will continue on the same dose with weekly evaluation for tolerability, hypotension and hyperkalemia.

[figure not shown]
At 4 weeks, participants randomized to the 50 mg SPL arm will increase the dose to 50 mg if the 25 mg dose was tolerated with weekly evaluations for tolerability, hypotension and hyperkalemia.

until 6 weeks. Participants randomized to 12.5 mg, 25 mg, or placebo will continue on the same dose with weekly evaluation for tolerability, hypotension and hyperkalemia until 6 weeks.

In order to maintain the blind, during the dose escalation phase all study participants, regardless of randomized assignment, will receive new study drug kits every 2 weeks and will be evaluated weekly.

At the end of the dose escalation phase, participants will continue treatment based on the randomized dose assignment for an additional 30 weeks (treatment phase) such that the total duration of study medication is 36 weeks. As described in **Sections 6.8 and 6.9**, the dose of SPL or placebo will be decreased during the dose-escalation and follow-up phases for hypotension, hyperkalemia or other dose limiting side-effects.

Figure 1. Study Design

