6.9. Hyperkalemia Management

[figure not shown]
Serum potassium will be measured at 3-5 days and 2 weeks after study drug initiation or dose increase as well as monthly throughout the duration of treatment. In order to minimize the risks of hyperkalemia, all participants will be provided with standardized, routine printed dietary information about dietary sources of potassium at the Baseline/Randomization visit. Treating clinicians will continue to manage the dialysate potassium concentration according to local standards. A hyperkalemia management guideline will be provided to treating clinicians. Study staff will monitor potassium values and contact treating clinicians in the event of hyperkalemia to review the management guidelines and ensure that hyperkalemia is being actively managed. Treating clinicians will be free to manage hyperkalemia according to local standards. However, study drug dose reductions or discontinuation will be directly managed by study investigators in accordance with the Hyperkalemia Management algorithm (see **Figure 2**).

As shown in **Figure 2**, study drug will be discontinued if serum potassium is ≥ 7.0 mEq/L. Study drug will also be discontinued if a 3rd study drug dose reduction is required. Study drug dose will be reduced if serum potassium is 6.0 – 6.9 mEq/L and either a) remains ≥ 6.5 mEq/L on repeat measurement or b) remains ≥ 6 mEq/L on repeat measurement despite a dialysate potassium bath concentration of ≤ 2.0 mEq/L. Reversible causes of hyperkalemia should be considered and addressed when serum potassium is ≥ 6.0 mEq/L even if there are changes to study drug dosing. Reversible causes of hyperkalemia include vascular access dysfunction, missed dialysis sessions, shortened or technically compromised dialysis sessions, dietary indiscretion and ACEI or ARB use. In general, these reversible causes should be addressed prior to reducing the dialysate potassium concentration. Use of 1.0 mEq/L dialysate potassium is not recommended. However, treating clinicians are not prohibited from using low potassium dialysate solutions in accordance with local practices. Serum potassium will be rechecked within one week when potassium is ≥ 6.0 mEq/L. Results of serum potassium and recommendations for change in dialysis orders will be conveyed to treating clinicians and the dialysis unit nursing staff.

CONFIDENTIAL

Do not disclose or use except as authorized by the Hemodialysis Novel Therapies Consortium.

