7.3. Intent-to-treat Analysis and Missing Data

An intent-to-treat analysis, in which all available data on all randomized participants are included, will be used for the primary comparison of treatments. All attempts will be made to keep missing data to a minimum, and participants who withdraw from treatment will be encouraged to continue on study in order to provide complete follow-up information. Thus, irrespective of withdrawal from treatment, all participants should continue to be followed with all scheduled outcome evaluations until the end of the study. However, it is expected that up to 10% of the randomized participants may withdraw prior to the final assessment of response at 36 weeks. These participants will be included in the denominator for evaluation of the response rates defined for the primary endpoint.

The characteristics at the time of randomization for those participants without complete follow-up will be examined; however, there will be limited statistical power to detect any but major differences between these participants and those with complete follow-up. In addition, in order to assess the potential biases introduced by differential withdrawal among treatment arms, a comparison of withdrawal rates and/or time to withdrawal will be included as an ancillary analysis to the primary endpoint comparison.

Secondary analyses will examine the all-treated, as-treated, and per-protocol populations as defined below:

- All-randomized population/intention-to-treat (ITT): Any participant randomized into the study, regardless of whether they received study drug.
- As-treated population: Any participant randomized into the study regardless of whether they received study drug. As-treated participants will be analyzed according to the dose of study drug actually received.
- All-treated population: Any participant randomized into the study that received at least one dose of study drug.
- Per-protocol population: Any participant who was appropriately randomized, and received the protocol-dictated study drug exposure ($\geq 75\%$ of prescribed doses) and endpoint assessments through 36 ± 2 weeks.

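### Safety analyses are to be repeated in a per-protocol set whose entry conditions depend on safety outcomes, so those secondary results can understate harm

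*Combined protocol and SAP*

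**What the plan says.** Section 7.4.1 sets the main population: "The primary analysis will examine the intention to treat population". It then adds that "All analyses will be repeated in the as-treated, all-treated and per-protocol populations". It treats secondary endpoints with analogous techniques and applies the 0.05 significance threshold to every analysis. Safety is not excepted.

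Section 7.3 gives the other sets secondary status: "Secondary analyses will examine the all-treated, as-treated, and per-protocol populations as defined below". A per-protocol participant must have been appropriately randomized, must have "received the protocol-dictated study drug exposure" (at least 75%), and must have the endpoint assessments: "of prescribed doses) and endpoint assessments through 36 ± 2 weeks".

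Section 6.9 links drug exposure to a safety outcome: "study drug will be discontinued if serum potassium is" at or above 7.0 mEq/L, and also when a third dose reduction is needed. Persistent potassium of 6.0 to 6.9 mEq/L leads to a dose reduction.

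Section 6.6.1 keeps participants who stop drug in follow-up and asks them to attend Week 36.

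**The concern.** A per-protocol set makes sense for E' and the other efficacy measures, where the question is what the drug does in people who took it and were measured. For safety, the entry conditions are partly consequences of the endpoint. Death prevents the Week 36 assessment. Severe hyperkalemia stops the drug, and so can repeated dose reductions for hypotension, an unexplained rash or intolerance (Sections 6.8, 6.10 and 4.4.2). A table built on participants who met both conditions leaves out some of those who were harmed.

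Section 7.1 puts the primary focus on safety and feasibility, and Section 1.1 expects the trial to inform the choice of dose. A per-protocol safety comparison carrying a formal significance label, with 25 participants per dose, could be read as reassurance. Section 7.3 argues for the as-treated safety analysis but gives no reason for a per-protocol one.

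**Working it through.** **The plan's nearest figure.** Section 7.1 gives 80% power for hyperkalemia at 5% on placebo against 22% pooled over spironolactone (SPL), with 50 and 75 participants. With unpooled variance, two-sided 0.05 (sidedness assumed) and 10% dropout (45 and 67.5):

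z = 0.17 / √(0.05×0.95/45 + 0.22×0.78/67.5) − 1.96 = 0.17/0.0600 − 1.96 = 0.87, so power is 80.9%.

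The figure reproduces and is not in dispute. The 5% and 22% are borrowed below for illustration only; 22% is a detectable rate, not an expected one.

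**Exposure threshold.** Section 3.1 describes daily dosing "such that the total duration of study medication is 36 weeks". That is 36 × 7 = 252 doses; 0.75 × 252 = 189 doses; 189/7 = 27 weeks.

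**Assessment threshold.** The window opens at 36 − 2 = 34 weeks.

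**Who is in the set**

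| Participant | Per-protocol status |
|---|---|
| Dies before about week 34 | Out under any reading |
| Withdraws without an assessment in the window (an Early Withdrawal visit before week 34 falls outside it) | Out under any reading |
| Drug stopped before about week 27, attends Week 36 | Out if *prescribed* means 252 doses; can be in if only doses up to the stop count |
| Drug stopped after week 27 with full adherence, attends Week 36 | In |
| Potassium >6.5 but <7.0 mEq/L, dose reduced, takes the reduced doses, attends Week 36 | In |
| Dies after the Week 36 assessment, before Week 40 | In, and counted |

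**Illustration of direction.** Let q be the share of participants with an event who leave the set, and assume 10% of event-free participants leave. Neither figure for leaving the set is in the documents. For SPL at q = 50%: events 0.22 × 75 = 16.5, kept 8.25; event-free 58.5, kept 52.65; displayed incidence 8.25/60.9 = 13.6%. For placebo: 1.25/44.0 = 2.8%.

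| q, same in both arms | Placebo | SPL | Difference (points) |
|---|---|---|---|
| 0% | 5.5% | 23.9% | 18.3 |
| 25% | 4.2% | 19.0% | 14.8 |
| 50% | 2.8% | 13.6% | 10.7 |
| 75% | 1.4% | 7.3% | 5.8 |

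The percentages and their difference shrink, but the odds ratio does not. It is (0.22/0.78)/(0.05/0.95) = 5.36 in every row, because an equal q cancels. Section 7.4.1 plans logistic regression, so that estimate moves only if q differs by arm (event-free losses held equal): it is multiplied by (1 − q on SPL)/(1 − q on placebo). With 50% on SPL and 25% on placebo it is 5.36 × 0.50/0.75 = 3.57; with the shares swapped it is 5.36 × 0.75/0.50 = 8.04.

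**The case against.** The strongest reply is that the plan already contains the damage. ITT is primary and the per-protocol set is secondary. Section 7.3 itself calls ITT the least-biased approach and names the as-treated analysis, by dose at the time of the event, as the supplement for dose-related adverse events. The all-treated results appear as well, so the full harm data sit beside any per-protocol table. Nothing in the plan gives the per-protocol set a role in choosing a dose. All of this stands, and it limits the severity.

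A reader might also infer more than the text supports:

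- **That entry requires completing the drug.** The rule is at least 75% of prescribed doses.
- **That many hyperkalemia events are removed by construction.** The primary endpoint is potassium >6.5 mEq/L, while Section 6.9 mandates a stop only at 7.0 mEq/L or above or at a third reduction. Events between 6.5 and 7.0 can stay in.
- **That tolerability will look near-perfect.** Any dose reduction is a tolerability failure (Section 3.2.1), and dose-reduced participants are not excluded. Early discontinuations are what can disappear. Section 7.4.1 describes no tolerability analysis, so tolerability is reached only through the words *all analyses*.
- **That per-protocol deaths are zero by definition.** Events are tracked for 4 weeks after the last dose (Section 8.2), so a death after the Week 36 assessment still counts.
- **That the attenuation can be quantified.** The exclusion shares above are assumptions, and equal shares leave the planned odds ratio unchanged.

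**Conclusion.** The concern holds in a limited form. The plan repeats safety analyses in a set selected on exposure and on reaching an assessment, both of which safety outcomes can alter. Exclusion of deaths and withdrawals before the assessment holds under every reading. Exclusion of drug stops before about week 27 rests on reading *prescribed* as the full 36-week regimen, which Section 7.3 does not settle. Displayed incidences of death, hospitalization, hyperkalemia, hypotension and discontinuation can therefore be too low, more so where stops are more frequent. Whether the odds ratio is also diluted depends on how exclusions differ by arm. The size of the bias cannot be computed from the documents. It is confined to secondary analyses, so severity is minor to moderate.

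**What to change.** Replace the sentence on repeat populations at the end of Section 7.4.1 with text such as:

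> Efficacy analyses will also be run in the as-treated, all-treated and per-protocol sets. Safety analyses will also be run in the all-treated and as-treated sets (Section 7.3) only. Tolerability and feasibility will be analysed in the ITT set. No safety or tolerability endpoint will be analysed in the per-protocol set.

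This keeps ITT as primary and preserves the as-treated safety analysis that Section 7.3 regards as critical. Because the per-protocol set remains in use for efficacy, Section 7.3 should also say whether the 75% is counted against all 36 weeks or only up to a stop.

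The cost is a few sentences and the loss of some secondary tables. No new data are needed.
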